### **12.2.5 Reporting Serious Adverse Events**

When an SAE is discovered, it will be reported immediately (within 24 business hours of the site's knowledge of the event) to the Sponsor/CRO Medical Monitor. Reportable events which do not meet the criteria for an SAE will include (but will not be limited to): (a) pregnancy, and (b) clinically significant (in the judgment of the investigator) severe psychiatric complications.

The eCRF will provide a mechanism for sites to report SAEs, and for investigators and the Medical Monitor to sign off on the SAE reports.

Reportable SAEs will be sent to the FDA by the sponsor and sites will be notified. Sites are responsible for submission of SAE reports to their IRB(s), in accordance with IRB policies.

### **12.2.6 Anticipated Serious Adverse Events**

Tan et al (2021) publication Identifying Anticipated Events of Future Clinical Trials by Leveraging Data from the Placebo Arms of Completed Trials looked at 18 Randomized, double-blind, controlled trials of Bipolar Depression that met similar inclusion and exclusion criteria to identify the most common Serious Adverse Events.

Based on this publication, the anticipated Serious Adverse Events are:

- Hospitalization, psychiatric symptoms
- Suicidal behavior, overdose
- Cholecystitis
- Fall
- Road traffic accident, injury

### **12.2.6.1 Overdose**

Overdose of the investigational product will be considered an SAE, even when there are no symptoms or additional AEs, and will be reported according to the guidelines in Section 12.2.5. An overdose associated with symptoms must be reported as an AE.

### **12.2.6.2 Suicidal Ideation and Clinical Management**

The documentation and proper management of suicidal ideation by sites will be documented with the use of the C-SSRS, completed by site clinicians during all visits. Safety will be evaluated throughout the course of the study.

Any patient who, based on the investigator's judgment, poses an imminent risk of suicide should be discontinued from the study. Suicide risk is assessed by the clinician at every visit.

Suicide, self-harm, and attempted suicide, irrespective of the method, will be reported as AEs (all suicides are SAEs; attempted suicides are considered to be SAEs). The event will be identified as suicide or attempted suicide, and the method of the suicide or attempt will be provided. If an attempted suicide meets the criteria for an SAE, the event must be reported according to the guidelines in Section 12.2.5. If a suicide attempt does not meet the criteria for an SAE, it will be considered a reportable AE, and a Suicidal Ideation or behavior Reportable Event Form will be completed by the investigator and submitted in accordance with the SAE reporting procedure in Section [12.2.5](#).

### **12.2.6.3 Pregnancy**

If a patient (or patient's partner) becomes pregnant during the study, it must be reported within 24 business hours of the time the investigator becomes aware of the event and in accordance with the procedures described on the Pregnancy Report Form. Although pregnancy itself is not regarded as an SAE/AE, unless there is a suspicion that a study drug may have interfered with the effectiveness of a contraceptive medication, the pregnancy details will be captured in the AE/SAE module of the eCRF. Any pregnancy that occurs from Visit 1 to 30 days following the last dose given will be followed for gestational outcome, and the outcome will be reported to the sponsor. The female patient will be discontinued from investigational product, but will continue to attend study visits for the duration of her participation in the study.

## **12.3 Concomitant Medications, Therapies, and Alcohol Restrictions**

### **12.3.1 Concomitant Medications**

Lurasidone is contraindicated with the use of strong CYP3A4 inhibitors (e.g., ketoconazole) and strong CYP3A4 inducers (e.g., rifampin) (see Appendix 1). The lurasidone dose should not exceed 40 mg/day if co-administered with moderate CYP3A4 inhibitors. There are no known reported interactions between DCS and lurasidone.

It is anticipated that participants entering the study will be receiving concurrent disorder-directed treatment with various combinations of medications, including:

- Approved antidepressants (e.g., SSRIs, SNRIs, TeCAs, fluoxetine), but not 5-HT-2A antagonists (lurasidone, aripiprazole, olanzapine/fluoxetine, quetiapine, cariprazine, or lumateperone)
- Mood stabilizers (e.g., lithium, valproic acid, and lamotrigine)

Participants will be permitted into the study if they are treated with no more than one drug from each category of the indicated classes. Approved antidepressants and mood stabilizers will be maintained at stable dosages throughout the study. This is both to ensure continued treatment and to prevent withdrawal symptoms that may occur if such drugs are rapidly discontinued. Participants—taking aripiprazole, risperidone, brexpiprazole, lumateperone, olanzapine, cariprazine, or quetiapine will discontinue these medications prior to Randomization in order to avoid overlap with lurasidone.

Allowed concomitant medications include any prescription or over-the-counter medication not specifically excluded by the protocol (see Appendix 1), as well as stable, ongoing antidepressant or mood stabilizer therapy and stable allowed hypnotic therapy. Participants requiring excluded medications will be discontinued from the study and an Early Termination Visit will be performed in accordance with Protocol Section 9.1.3.

Prohibited concomitant medications that the patient and the investigator agree to discontinue for the purpose of study entry will be washed out for a period defined by the Investigator in consultation with the Medical Monitor. In the event concomitant medication washout is appropriate for a patient per investigator judgment, the patient must sign the informed consent form prior to beginning the washout period. Clinically appropriate tapering regimens should be used, if applicable. The Screening period may be extended, upon consultation with the Medical Monitor, to allow for a sufficient washout period.

All concomitant medications taken during the study and 4-weeks prior to study entry will be recorded in the electronic case report form (eCRF) for each patient, along with dosage information and start and stop dates.

### **12.3.2 Concomitant Therapy**

Participants receiving concurrent psychotherapy that has been stable in type and frequency (e.g., weekly, monthly) for at least 3 months prior to Screening are eligible for study entry if the psychotherapy is expected to remain stable for the duration of the patient’s participation in the study. Any changes in psychotherapy type and/or frequency during the study should be discussed with the Medical Monitor as soon as the investigator is aware of the proposed change.

### **12.3.3 Alcohol Restrictions**

Participants should not use alcohol during the study. Ethyl alcohol may increase the possibility and risks of seizures in participants with a history of alcoholism receiving cycloserine.

### **12.3.4 Positive Drug Screen**

Participants who have a positive urine drug screen two times in a row for use of any cocaine, opiates and non-prescribed amphetamine and non-prescribed barbiturates will be withdrawn from the study.

### **12.4 Laboratory/Diagnostic Procedures**

Clinical laboratory safety testing will be performed locally at the study site using a Clinical Laboratory Improvement Amendments (CLIA)-certified laboratory. The frequency and type of procedures are detailed in the Schedule of Assessments (

**Table 1).** Local laboratory normal ranges must be reported according to gender.

Participants will have their blood drawn for clinical chemistry (ALT, AST, GGT, ALK phosphatase, Creatinine, T4, T3, TSH, Albumin, BUN, Calcium, Sodium, Potassium, Chloride, Glucose, Total Bilirubin, Direct Bilirubin, Total Protein, Total Cholesterol, HDL/LDL, Triglycerides, Uric Acid, HbA1c) and hematology testing (Red blood cell count, White blood cell count, Platelet count, Hemoglobin, Hematocrit, Neutrophils Absolute or percent, Lymphocytes Absolute or percent, Monocytes Absolute or percent, Eosinophils Absolute or percent, Basophils Absolute or percent). Urine sample testing for pregnancy and drug screen will be by dipstick. In the event of clinically significant abnormal laboratory test result(s), follow-up laboratory testing may be conducted, at the discretion of the investigator. If applicable, clinically significant changes from baseline in laboratory results will be noted as AE(s), in accordance with Section 12.2.1.

### **12.5 Physical Examinations, Vital Signs, Height, and Weight**

Physical examinations, vital signs, height, and weight will be obtained at the noted visits. Vital signs (blood pressure and heart rate) may be repeated 15 min apart, as needed, in order to obtain a resting reading. If applicable, clinically significant changes from baseline in physical examination parameters, vital signs, and weight will be noted as AE(s), in accordance with Section 12.2.1.

### **12.6 Electrocardiograms**

Twelve-lead ECGs will be obtained after the patient has been resting in a semi-recumbent position for at least 5 minutes. All digital ECGs will include the date and time obtained, heart rate, QRS duration, PR interval, RR interval, QT interval, and QTcF interval using Fridericia formula (Puddu et al., 1988). If indicated, additional ECG assessments may be performed, at the discretion of the investigator. If applicable, clinically significant changes from baseline in ECG assessments will be noted as AE(s), in accordance with Section 12.2.1.

## **12.7 Study Monitoring by the Drug Safety Monitoring Board (DSMB)**

The study will be monitored for safety, futility, and efficacy by a DSMB. Interim analysis for safety will be conducted six weeks after the first 30-35 participants complete Day 42 based on reported Adverse Events and Serious Adverse Events. The study may be stopped for safety concerns. A second DSMB assessment for safety and futility will be conducted when 45-50 participants have reached Day 42.

## **13. REGULATORY STANDARDS**

The study analyses will be conducted in a GCP environment (ICH E6 and E9 [R1]). All analyses will be pre-specified and finalized prior to database lock. If the methods in this SAP do not agree with the protocol, the methods described in the SAP will govern the analysis.

## **14. RANDOMIZATION**

Randomization will be stratified by evidence of a suicidal event in the prior 12 months (none, any). Investigational product for oral administration (NRX-101 or lurasidone) will be provided as blinded kits to sites for dispensing to subjects. Packaging will contain coded and blinded bottles with capsules of identical size, shape, and color irrespective of the study arm to which a subject is randomized. Storage

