Statistical Methods:	
All randomized participants will be evaluated for depression (MADRS), suicidality (C-SSRS), and other efficacy endpoints while on the study. Analyses will be conducted under ICH E9 (R1) guidelines. C-SSRS is a safety endpoint.
 
Change from baseline in MADRS total scores through study exit to compare treatments will be analyzed using Mixed Model Repeated Measures analysis (SAS PROC MIXED) with Last Observation Carried Forward (LOCF) containing sex, baseline use of mood stabilizers, baseline use of anti-psychotics, BPRS rating scale (none, any) and evidence of a suicidal event in their lifetime (none, any) as stratification factors in the analysis. Additional analyses will alternatively rely on multiple imputation to assess the impact of dropouts. The NRX-101 and lurasidone treatment groups will be compared using stratified and unstratified log rank tests, as well as a proportional hazard model for time to relapse.

Sample Size Calculation:	Participants will be randomized in a 1:1 ratio (NRX-101:lurasidone). With 37 participants per group, there is an 80 percent power to detect a mean 8.85-unit advantage for NRX-101 vs lurasidone for the CFB to Day 42, assuming a SD of 13.4 for NRX-101 versus lurasidone at 6 weeks for a two-sided hypothesis test with two-sided 5 percent Type I error. This equates to a 0.66 effect size.
Interim Analysis	
Two interim analyses are planned. The first interim analysis (IA) assessing safety will be conducted six weeks after the first 30-35 participants have been followed for 6 weeks and the second IA assessing futility (primary efficacy endpoint) will be performed after the first 45-50 participants have reached 42 days post-randomization.
 
Each interim analysis has a different objective with neither interim analysis spending any Type 1 error. The study will be stopped at the first interim analysis if Serious Adverse Events are deemed statistically significantly more common in the NRX-101 group compared to the lurasidone group in a manner deemed by the DMC to pose a potential danger to human subjects. The study will be stopped at the second IA for futility if the conditional power (CP) is less than 10%. In the event that the study is not stopped for either safety or futility, then enrollment will continue until a total of 74 subjects are randomized. This preserves two-sided <math>p=0.05</math> for the final analysis.

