### 10.2 Bipolarity Index (BPI)

BPI was not collected in this study. The BPRS will be used instead of the BPI to rate the cardinal features of bipolar disorder across five domains: episode characteristics (signs and symptoms); age of onset (first episode); course of illness; response to treatment; and family history.

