### 16.3 Secondary Hypotheses

The secondary hypothesis are that:

- treatment with NRX-101 is superior to lurasidone in improving symptoms of suicidality as measured by the CGI-SS over 6 weeks of treatment. The null hypothesis is the mean change from baseline of CGI-SS for NRX-101 is greater than or equal to the mean change from baseline of CGI-SS for lurasidone while the alternative hypothesis is that the mean change from baseline of CGI-SS is less than the mean change from baseline of CGI-SS for lurasidone (improvement). Baseline is defined as CGI-SS score at this study entry.
- that NRX-101 is superior to lurasidone in time to treatment failure as defined as: study discontinuation due to Adverse Events; psychiatric hospitalization; or requiring a change in antidepressant treatment. Time to treatment failure may be ascertained as the treating physician's determination of a study discontinuation due to lack of efficacy; withdrawal due to a treatment related adverse event a psychiatric hospitalization; or the patient requiring any change in their baseline antidepressant, mood stabilizer, or antipsychotic medication. Titration or change in timing of administration of study medication will not be considered a failure of therapy. Lack of efficacy is defined as the need to implement a new treatment plan or an increase in suicidal ideation (a score of 4 or 5 on the C-SSRS, emergent suicidality requiring hospitalization), or increase in depressive symptoms (a score increase of  $\geq 5$  for two consecutive visits on the MADRS total score). The need to implement a new

treatment plan includes the addition of new antidepressant medication or somatic treatment (e.g. ECT or rTMS treatment) or an escalation of care such as hospitalization (i.e. moving the patient from outpatient care to initiating inpatient, partial or day hospitalization). Time to failure will be assessed using a Kaplan-Meier lifetable. The formal hypothesis test will be to detect a 0.421 hazard ratio (HR) with 80% power for a two-sided test using a proportional hazard model; a 0.545 hazard ratio reaches two-sided  $p=0.05$ .

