#### 19.4 Estimand Structure

Analyses will be conducted in accordance with ICH E9 (R1) analysis principles as summarized below.

Primary scientific question of interest	The primary study hypothesis is that treatment with NRX-101 is superior to lurasidone in improving symptoms of depression as measured by the MADRS over 6 weeks of treatment. The null hypothesis for the primary endpoint is the mean change from baseline of MADRS-10 for NRX-101 is the same as lurasidone while the alternative hypothesis is that the mean change from baseline of MADRS-10 is larger than the mean change from baseline of MADRS-10 for lurasidone. Baseline is defined as MADRS-10 score at Visit 2 (randomization).
Target population	The mITT population will be the primary analysis population. The mITT population is defined through appropriate inclusion/exclusion criteria as specified in the protocol and blinded BDRM decisions.
Treatment of interest	NRX-101
Outcome Variables	MADRS-10 (and C-SSRS) will be recorded as audio files and reviewed by central master-raters with any non-congruent subject-visits from any site with >10% non-congruent scores sent to a qualified independent adjudicator to be considered as the subject-visit primary study endpoint.
Summary Measure	The contrast-estimated MADRS-10 Week 6 MMRM will use all post-randomization data with LOCF in the mITT population excluding all outcomes after BDRM-approved exclusions. The model will include treatment and the following four baseline covariates in addition to baseline MADRS-10: (1) sex, (2) mood stabilizer use, (3) anti-psychotic use, and (4) evidence of suicide event in their lifetime. The model will include treatment group, study visit, the interaction between study visit and treatment group, baseline MADRS-10, and the four baseline covariates as fixed effects. An unstructured error structure will be assumed.
Intercurrent Events	A BDRM will adjudicate all intercurrent events which may redact outcomes after disqualifying events; these intercurrent events may represent major protocol deviations.

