## 20. STATISTICAL METHODOLOGY

### 20.1 General Methodology

The Mixed-Effect Model Repeated Measure (MMRM) will be the primary analysis for the primary efficacy endpoint (MADRS change from baseline); an unpaired t-test will be a secondary analysis. The proportional hazard model (PHREG) will be the primary analysis for time to event endpoints (time to remission, time to discontinuation); the unstratified log rank test will be a secondary analysis. The MMRM and PHREG models will all include treatment and the following four baseline covariates:

- sex
- mood stabilizer use
- anti-psychotic use
- evidence of suicide event in their lifetime.

All primary analyses will be in the mITT population as primary and repeated in the Per Protocol population if >5 percent are excluded.

All of the instruments used to measure SSIB or depression constitute serial continuous and ordinal outcomes that will be analyzed using MMRM with LOCF to account for missing data and early discontinuations. The models will include treatment group, study visit, the interaction between study visit and treatment group, the baseline level of the variable being analyzed, and the above four pre-defined baseline stratification factors as fixed effects. The primary endpoint change from baseline MADRS-10 will be analyzed using the MMRM model which will include baseline MADRS; treatment group; study visit; study visit\*treatment; sex, mood stabilizer use, anti-psychotic use, and evidence of suicide event in their lifetime as defined above. An unstructured error structure will be assumed.

SAS PROC MIXED will be used for continuous endpoints.

In addition, supportive analyses will be performed using multiple imputation which will be performed to address any missing data. The method of Little and Rubin will be used. The presentation of the results for the primary efficacy endpoints using the ITT population will be based on the observed data with multiple imputation for missing endpoint data using SAS PROC MI. Missing data will be imputed using MCMC imputation under the assumption of a missing at random using the mITT population. The SAS® procedure PROC MI will be used for the MCMC imputation of 25 complete data sets.

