### **20.3 Secondary Efficacy Endpoints**

All of the instruments used to measure SSIB or depression constitute serial continuous and ordinal outcomes that will be analyzed using MMRM with LOCF, which accounts for missing data and early discontinuations. Results will be presented separately for each treatment group.

The models will include treatment group, study visit, the interaction between study visit and treatment group, the randomization baseline of the variable being analyzed, and the four baseline stratification factors as fixed effects. The reason for missing data will be evaluated as a condition of MMRM analysis.

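### The 12-month suicidal-event stratum used for randomisation is in no MMRM or proportional hazards model, and the SAP synopsis and body list different covariates for the primary model.

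*SAP*

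**What the plan says.** **Randomisation.** SAP 14 states: "Randomization will be stratified by evidence of a suicidal event in the prior 12 months (none, any"). Protocol 16.1 is identical. No other stratification factor is named.

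**Models in the SAP body.** The estimand table in SAP 19.4 lists sex, mood stabilizer use, anti-psychotic use and, as the last item, "4) evidence of suicide event in their lifetime", in addition to baseline MADRS-10. SAP 20.1 extends the same set to everything: "The MMRM and PHREG models will all include treatment and the following four baseline covariates". SAP 20.2 refers back to that list for the other time-to-event models. SAP 20.3 refers to "the four baseline stratification factors as fixed effects" for the secondary endpoints.

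**Model in the SAP synopsis.** The Statistical Methods entry names sex, mood stabilizers and anti-psychotics and then "BPRS rating scale (none, any) and evidence of a suicidal event in their lifetime (none, any) as stratification factors in the analysis". That makes five factors, one more than the body.

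**Related text.** SAP 10.2 says that the BPI was not collected and that "The BPRS will be used instead of the BPI to rate the cardinal features of bipolar disorder". SAP 13 gives one precedence rule: "If the methods in this SAP do not agree with the protocol, the methods described in the SAP will govern the analysis". It does not rank the synopsis against the body. Neither document defines a suicidal event for the purpose of stratification.

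**The concern.** There are two separate defects.

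1. **The design factor is not in the analysis.** Stratified randomisation balances the arms on the stratum. If the stratum is prognostic and is left out of the model, the variance it explains stays in the residual. The standard error is then too large for the design, so the test is somewhat conservative and loses power. In a linear model the estimate remains unbiased. In a proportional hazards model, omitting a prognostic factor also moves the estimated hazard ratio towards 1. The lifetime flag does not cure this: everyone with a 12-month event has a lifetime event, but not the reverse.

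2. **The primary model is not uniquely specified.** A programmer working from the synopsis fits BPRS; one working from 19.4 or 20.1 does not. The BPRS entry cannot be dismissed as a slip, because the protocol synopsis has BPI in that position and SAP 10.2 substitutes BPRS for BPI. If this is settled after unblinding, it becomes a post hoc choice between two primary analyses.

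**Working it through.** **1. The plan's own figures reproduce.** With 37 per arm, d = 8.85/13.4 = 0.66 and two-sided 5%, noncentral-t power on 72 df is 0.800 (stated 80%). The smallest significant d is t(0.975, 72) × √(2/37) = 0.463 (stated 0.462). For time to treatment failure, SAP 16.3 aims to "detect a 0.421 hazard ratio (HR) with 80% power for a two-sided test using a proportional hazard model". The events this implies are 4(1.960 + 0.842)²/(ln 0.421)² = 41.9. The stated critical hazard ratio of 0.545 implies 4(1.960)²/(ln 0.545)² = 41.7. Both give about 42 events in 74 patients, a count the documents do not state. None of these calculations uses a stratum.

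**2. Assumptions for the omitted stratum.**
- 12-month event rate p = 10–20%. This is not in the documents.
- Lifetime rate L = 25–56%. This is the range in SAP 6.1 for suicidal behaviour in bipolar disorder generally, not for this trial.
- Stratum gap g in the MADRS change of 0.3, 0.5 or 0.8 SD, that is 4.0, 6.7 or 10.7 points at SD 13.4. The last exceeds the 8.85-point target effect, so it is an upper end.

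**3. MMRM, closed form.** This uses a single-visit approximation without the other covariates.
- Share of outcome variance explained by the stratum: R² = g²p(1−p).
- Share of that recovered by the lifetime flag: φ² = p(1−L)/[L(1−p)].
- Power is from the noncentral t on 71 df, with d = 0.66/√(1−R²) if the stratum is fitted and d = 0.66/√(1−R²φ²) if the lifetime flag is fitted.

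The smallest loss is at p = 0.20, L = 0.25, where φ² = (0.20 × 0.75)/(0.25 × 0.80) = 0.75. The largest is at p = 0.20, L = 0.56, where φ² = (0.20 × 0.44)/(0.56 × 0.80) = 0.20.

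| g (SD) | R² at p = 0.20 | Power, lifetime vs stratum (smallest loss) | Power, lifetime vs stratum (largest loss) | Loss, points |
|---|---|---|---|---|
| 0.3 | 0.014 | 0.8039 vs 0.8053 | 0.8007 vs 0.8053 | 0.1–0.5 |
| 0.5 | 0.040 | 0.8114 vs 0.8154 | 0.8027 vs 0.8154 | 0.4–1.3 |
| 0.8 | 0.102 | 0.8300 vs 0.8403 | 0.8075 vs 0.8403 | 1.0–3.3 |

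**4. MMRM, simulation check.** The check used ANCOVA on one visit, blocks of 4 within stratum and 10,000 trials per cell. Losses were 0.4–0.7, 0.4–1.7 and 1.1–2.9 points at the three gaps. Type I error with the lifetime flag was 0.044–0.053, and the mean estimation error was at most 0.005 SD. The Monte Carlo standard error of one power figure is 0.4 points.

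**5. A stronger stratum.** If R² were 5%, 10% or 20% and neither flag were fitted, the actual two-sided alpha would be 2[1 − Φ(1.96/√(1−R²))] = 0.044, 0.039 or 0.028. Power (normal approximation) would be 81.6% vs 83.0%, 82.3% vs 84.9% or 83.7% vs 88.8%, omitted versus included. The direction is the same: conservative, not inflated.

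**6. Proportional hazards, simulation.** True hazard ratio 0.421, 42 events, exponential times, the same randomisation, L also at 40%, and 10,000 trials per cell:

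| Stratum hazard ratio | Power loss, points | Largest-loss cell, lifetime vs stratum | Shift of estimated HR towards 1 |
|---|---|---|---|
| 1.5 | 0.5–1.3 | 0.771 vs 0.784 | 0.001–0.004 |
| 2 | 0.8–2.5 | 0.766 vs 0.790 | 0.004–0.012 |
| 3 (upper end) | 2.5–5.2 | 0.737 vs 0.789 | 0.011–0.030 |

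Type I error was 0.040–0.052 with the lifetime flag and 0.042–0.054 with the stratum.

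**7. Definition.** If a suicidal event includes ideation, inclusion criterion 10 (active ideation within 4 weeks of screening) makes nearly every patient positive on both flags, and the loss is about zero.

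**8. Covariate lists.** The synopsis has five factors, including BPRS. SAP 19.4 and 20.1 list four and 20.3 refers to four, all without BPRS. The synopsis also does not mention baseline MADRS-10, which the body includes.

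**The case against.** The strongest reply is that 12 months and lifetime may be two wordings of one intended factor. The SAP repeatedly calls its covariates stratification factors, and the documents cannot show what the randomisation system used. If it used the lifetime event, the factor is already in the models and only SAP 14 is wrong. That possibility is real and the fix has to cover it, but the label does not put the 12-month variable into any model, and both documents name that variable for randomisation.

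Second, the effect is small and its inputs are assumed. This stands. A repeat simulation of the largest-loss MMRM cell (20,000 trials) gave about 1.0, 1.4 and 3.0 points against 0.5, 1.3 and 3.3 from the closed form, so the tenths should not be relied on. The calculations also leave out baseline MADRS and the other covariates.

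Third, the synopsis may simply be an abbreviated summary, as its silence on baseline MADRS-10 suggests. That is plausible, but an abbreviation would not add a term.

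Finally, the synopsis mentions a stratified log rank test where the stratum might enter. Its strata are not named, SAP 20.1 and 20.2 specify only unstratified tests, and it is neither the MMRM nor the proportional hazards model.

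**Conclusion.** The concern holds, as a minor one. As written, the randomisation factor is in no MMRM or proportional hazards model, and the SAP gives two covariate lists for its primary analysis with no rule to choose between them.

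The omission does not bias the MMRM estimate, inflate type I error or change the sample size. Under the assumed rates it costs up to about 1 power point in the MMRM for stratum gaps of 0.3–0.5 SD and about 3 points at 0.8 SD. For time to treatment failure it costs about 1 to 5 points, with a shift in the hazard ratio of at most 0.03. If ideation counts as an event, the cost is about nil.

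The inconsistent covariate lists need no such assumptions: they leave the primary model open until one list is fixed.

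**What to change.** 1. Add the stratum value as used at randomisation to the MMRM and proportional hazards models in the SAP synopsis, 19.4, 20.1 and 20.3. SAP 20.2 follows by reference.
2. Before unblinding, give one identical covariate list in all four places, including baseline MADRS-10 for the primary model. The simplest course is to align the synopsis with the body and drop BPRS. Whether the lifetime event stays as a further covariate is the sponsor's choice.
3. In SAP 14, define what counted as a suicidal event.
4. Confirm that the randomisation file holds the 12-month value. If it does not, correct SAP 14 to the factor actually used and put that factor in the models.
5. While editing, keep the term stratification factor for the randomisation factor, and either name the strata of the log rank test in the synopsis or delete that test.

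The cost is SAP wording and the merging of one value per patient from the randomisation file, whose availability must be confirmed. The sample size does not change.
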